9.1 End of Study

The end of the study will be the date of last subject's last visit.

10. Subject Population

The study population will comprise people with PD and mild dementia residing in the UK. The inclusion criteria have deliberately been kept as broad as possible to maximise recruitment and give the trial findings greater external validity.

Inclusion Criteria

- 1. A diagnosis of Parkinson's Disease according to the UK Parkinson's Disease Society Brain Bank Criteria ²⁷. These criteria are in standard use throughout the NHS in the UK and are supported by the NICE guidelines.
- 2. People with mild dementia associated with PD, where the patient and/or their family have become aware of cognitive problems with or without behavioural symptoms causing functional impairment. "Dementia" will be defined according to recently published Movement Disorder Society Task Force criteria for dementia associated with Parkinson's Disease ²⁸ and "operationalised" using the Addenbrooke's Cognitive Examination (ACE-R). The ACE-R permits some description of the dementia profile and also quantifies global impairment ²⁹. It is increasingly used by clinicians in the UK to identify demented subjects, is relatively quick to perform (15 minutes or so), requires no specific training and produces a total score (0-100), from which the MMSE (0-30) can also be extracted. Participants will have an ACE-R of 88 or less ²⁹. If this criterion is met, subjects will be further assessed using the Mattis Dementia Rating Scale (DRS-2). An age- and education-corrected total DRS-2 score of less than or equal to 8 but greater than or equal to 4 will be used to define "mild" dementia ³⁰.
- 3. Community living and a spouse, close relative or well established carer to accompany the subject to act as an informant.
- 4. Where relevant, women of child bearing potential must be using adequate contraception for duration of study.

Exclusion Criteria

- 1. Dementia that develops within one year of the onset of motor symptoms. The reason for this "one year rule" is specifically to exclude participants with Dementia with Lewy Bodies (DLB). This exclusion criterion is consistent with recommendations made in the Movement Disorder Society Dementia Task Force Diagnostic Criteria²⁸ and the Third Report of the DLB Consortium³¹.
- 2. People with such severe motor disability, or who are so impaired in their activities of daily living from other aspects of their PD, that it would interfere with cognitive and global assessments.
- 3. Severe current depressive episode. Low mood may impact upon accurate cognitive assessment, and major depression is therefore listed as a feature which, when present, makes it impossible to reliably diagnose PDD in the Movement Disorder Society Task Force PDD Criteria ²⁸. This will be operationalised using the self-completed Beck Depression Inventory and a cut-off score of 13, as recommended by a recent Movement Disorder Society Task Force report ³². The BDI score is considered robust in the face of mild to moderate cognitive impairment.
 Batients who have adiabatly similar domastical as highlighted by the BDI way he treated for

Patients who have clinically significant depression as highlighted by the BDI may be treated for their depression and potentially screened at a later date..

- 4. Unstable significant medical co-morbidity.
- Patient currently receiving a non-selective centrally acting anticholinergic drug for control of parkinsonian motor symptoms or other indication (eg urinary urgency) are EXCLUDED and use of these medication is forbidden throughout the duration of the study.

An 8-week washout is required should these agents be discontinued prior to study entry.

- 6. Previous exposure to any cholinesterase inhibitor excludes a patient.
- 7. Presence of a condition that is contraindicative to use of donepezil hydrochloride (including a clinically significant cardiac conduction defect found in patient history or from screening ECG); see Summary of Product Characteristics (SmPC) (Appendix A1 and 2) for details.
- 8. Allergy/hypersensitivity to excipients of donepezil hydrochloride or placebo.
- 9. Patient receiving the N-methyl-d-aspartate antagonist memantine; no exposure, previous or current, is permitted
- 10. Deep brain stimulation, or other neurosurgical procedure for Parkinson's disease, within 12 months of the screening visit.

Stable doses of atypical anti-psychotic medication (i.e. dose unchanged for 6 weeks prior to study entry) *will* be permitted. Many patients with PDD experience psychotic features (especially visual hallucinations) prior to the onset of cognitive decline which may require atypical anti-psychotic medication. It is felt that it would be both impractical and unethical to exclude the use, or require the withdrawal, of these agents in a placebo-controlled study.

11. Screening, Recruitment and Consent

11.1 Screening

Potential participants will be identified through routine outpatient appointments at trial sites and agreed participant identification centres. Where relevant, DeNDRoN staff will assist in the identification of potential participants in these clinics or screening of databases. All staff involved in identifying patients, with no direct bearing on the patients' care, will as a minimum have letters of access.

An eligibility screening form will be completed by the investigator to document fulfilment of the entry criteria for all patients considered for the study and subsequently included or excluded. Anonymised demographic details of those excluded will be recorded, to facilitate ascertainment of extent of participation bias, and reasons for exclusion will be recorded, insofar as is possible, to facilitate construction of the CONSORT diagram.

The screening assessments (as per routine clinical practice) will occur 2 weeks (+/- 2 days) prior to baseline visit, randomisation and start of study drug.

11.2 Recruitment

Eligible participants will be invited to participate by the site PI, or another member of site research staff with documented delegated responsibility, and the study explained to them. A study Patient Information Sheet will be provided at this time and the patient will be allowed to take this away for further consideration and discussion with significant others.

A screening log will be kept to document details of subjects invited to participate in the study. For subjects who decline participation, this will document any reasons available for non-participation. The log will also ensure that potential participants are only approached once.

11.3 Consent

Informed consent discussions will be undertaken by appropriately trained site staff (as per delegation log) involved in the study, including medical staff and research nurses, with opportunity for participants to ask any questions. Following receipt of information about the study, participants will be given reasonable time (a minimum of 24 hours) to decide whether or not they would like to participate. Those wishing to take part will provide written informed consent by signing and dating the study consent form. The principal investigator or another member of site research staff with documented delegated authority will counter-sign and date the consent form. Where the patient is unable to sign his/her name because of problems with literacy, or visual or motor impairments, verbal consent will be taken in the presence of an independent witness who will sign and date the consent form on behalf of the patient. Written informed consent should always be obtained prior to randomisation and prior to study specific procedures/investigations.

The original signed consent form will be retained in the Investigator Site File/Patient study folder, with a copy in the clinical notes and a copy provided to the participant. The participant will specifically consent to their GP being informed of their participation in the study.

The right to refuse to participate without giving reasons will be respected.

At the time of consent, all participants will have mental capacity. Capacity will be formally assessed using the MUSTARDD-PD Assessing Capacity Instrument prior to consent and at visit 5. Consent will also be obtained, however, from an informant (carer or close relative) at study entry. The informant will receive information about the study. This information will include a description of what is expected of them and will also explain their role, should the participant lose mental capacity during the course of the study. A back-up spokesperson and/or a Personal Consultee can be nominated by the participant at the time of entry into the study. A spokesperson/Personal Consultee is free to withdraw from the study at any time. The assistance of a back-up spokesperson should be sought if the original spokesperson withdraws or is no longer able to assist the participant.

Due to the small subject population, the information sheet and consent form for the study will be available only in English. Interpreters will be arranged for all visits of patients who require them either for verbal translation or for deaf subjects wishing to take part in the study, via local NHS arrangements. Qualified interpreters will be used to explain the consent form and information sheet, and great priority will be placed on finding the most direct communication.

12. Study Medication / Intervention Details

12.1 General Information

Donepezil hydrochloride is a centrally acting cholinesterase inhibitor; it is indicated for the symptomatic treatment of mild to moderate Alzheimer's dementia and is therefore being used outwith its Marketing Authorisation in this trial. It increases synaptic levels of the neurotransmitter acetylcholine by inhibiting the enzyme acetylcholinesterase. Given the strong convergent evidence that cognitive and neuropsychiatric symptoms are at least in part mediated by cortical and subcortical cholinergic deficits in PDD, there is therefore a clear rationale for the use of this agent in the context of this trial.

In MUSTARDD-PD 500 people with Parkinson's disease and mild dementia will be randomised to receive either donepezil hydrochloride or matching placebo in a 1:1 ratio. The use of a third arm (*i.e.* a second cholinesterase inhibitor such as rivastigmine, in addition to donepezil hydrochloride and placebo) was discounted since the sample size required to indicate any difference between active treatments would be unfeasibly large, while the clinical impact of any such difference would be likely to be negligible.

Donepezil hydrochloride was chosen, rather than rivastigamine or galantamine, because it is the most commonly prescribed cholinesterase inhibitor in the UK for all dementia syndromes, with 75-80% of the market share. The reasons for this may include ease of titration, once daily dosing and better tolerability, all of which are relevant to this study by potentially improving drug adherence and reducing attrition rate.

Donepezil hydrochloride is widely used in the UK for the treatment of Alzheimer's disease. Even though it is also used throughout the UK to treat PDD, this is an unlicensed indication. For the purposes of this study, donepezil hydrochloride will therefore be treated as an investigational medicinal product (IMP).

For reported side effects of donepezil hydrochloride please refer to section 19 Pharmacovigilance.

Donepezil hydrochloride, purchased by the Sponsor, has a shelf life of 3 years and should be stored below 30°C.

Please refer to the summary of product characteristics (Appendix A1 and 2) for more detail.

Blinding will be achieved by over-encapsulation.

The placebo will be gelatine capsules with microcrystalline cellulose.

12.2 Administration of Study Drug

Study medication will be labelled according to the requirements of Annex 13. All study medication for a particular site will be provided by Piramal to the site pharmacist following site initiation. Study medication will be for use by trial participants only. There will be study-specific prescriptions, and medication will be dispensed by the site pharmacist when the participant attends for their study assessments. Treatment will be taken on an out-patient basis.

Active and placebo study medication will be provided either as 5mg or 10mg capsules. Each participant pack will be presented as bottles in an outer carton.

Weeks 1-26:	5 bottles (5mg) for 5mg or 10 mg dose as directed by team caring for patient. If patient tolerates 5mg dose after 8 weeks then dose to be increased to 2×5 mg. If between week 9 and week 26 patient does not tolerate increased dose, it can be reduced back to 5mg.
Weeks 26-52:	2 bottles (10mg od)
Weeks 52-78:	2 bottles (10mg od)
Weeks 78-104:	2 bottles (10mg od)

The starting dose will be 5mg/day. All participants will be titrated up to 10mg/day after eight weeks. Side effects will be documented by the participant throughout the course of the trial and will be assessed by the clinical team by telephone contact prior to dose escalation from 5mg to 10mg. Any participant reporting significant side effects on 10mg donepezil hydrochloride/day may have their dose decreased back to 5mg/day, for a further two week period prior to attempting to re-escalate to 10mg/day.

A seven-day visit window is allowed for each 26 weekly dispensing visit. Each visit date should be planned from the date of T0, and not the previous visit.

Study medication will be prescribed by a study clinician according to the protocol, and dispensed to the patient or clinical staff according to local pharmacy policy. Patients in possession of their study medication shall return all trial supplies in their original packaging (even if empty) to the Pharmacist every 26 weeks. All returned, or unused, study medication will be stored in Pharmacy until the end of the study, or until the Trial Manager has completed appropriate reconciliation.

Documentation of prescribing, dispensing and return of study medication shall be maintained for study records.

At the end of the study, MUSTARDD-PD participants will be given the option to start donepezil hydrochloride through normal prescription starting at a dose of 5mg/day, titrated to 10mg/day after eight weeks. Those withdrawing prematurely from the MUSTARDD-PD trial will not be given this option. Donepezil hydrochloride prescribed at the end of the study must be supplied from normal local pharmacy stock. Alternatively, subjects may be given the option of being prescribed rivastigmine, a cholinesterase inhibitor licensed for use in dementia associated with PD.

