The purpose of this call is to record any adverse events that may have occurred on the study medication (placebo or donepezil hydrochloride 5mg per day) and check concomitant medications. This call will be made by the Study Nurse. If there are no adverse events that are deemed by the study team to be dose-limiting, then the subject will be requested to increase the dose as prescribed to 10mg per day of donepezil hydrochloride or matching placebo. *Ensure the patient records an increase in the dose on the study medication card.*

Visit 4: 26 weeks (± 7 *days*)

The following procedures and assessments will be carried out at this visit:

- 1. Mattis DRS-2
- 2. NPI-10 (administered to caregiver/informant)
- 3. BADLS (administered to caregiver/informant)
- 4. Modified ADCS-CGIC interview and scoring
- 5. Montreal Cognitive Assessment (MoCA)
- 6. Parkinson's Disease Cognitive Rating Scale (PD-CRS)
- 7. SCales for Outcomes of PArkinson's disease-cognition (SCOPA-cog) (administered to patient)
- 8. EQ-5D
- 9. DEMQOL and DEMQOL-proxy (latter administered to caregiver/informant)
- 10. Scale of Quality of Life of Caregivers (administered to caregiver/informant)
- 11. UPDRS
- 12. Client Service Receipt Inventory (assessing service use over preceding 6 months) (administered to caregiver/informant)
- 13. Activities-Specific Balance Confidence Scale (ABC)
- 14. Provision falls diaries
- 15. Review any adverse events
- 16. Check concomitant medications
- 17. Check study medication returned
- 18. Dispense study medication and medication card.

Note: Assessments 1-7 must be carried out by an independent rater (that is, an investigator who is unaware of the outcome of the other assessments to be performed at this visit, such as recording of adverse events, which could potentially un-blind the assessor). The participant should be requested not to discuss possible adverse events or interim problems with this rater prior to their assessments being performed.

Note: Ensure an adequate rest break is provided during the visit along with refreshments for the patient and the spokesperson.

Visit 5: 52 weeks (± 7 *days*)

The following procedures and assessments will be carried out at this visit:

- 1. Capacity Assessment
- 2. Mattis DRS-2
- 3. NPI-10 (administered to caregiver/informant)
- 4. Modified ADCS-CGIC interview and scoring
- 5. Montreal Cognitive Assessment (MoCA)
- 6. Parkinson's Disease Cognitive Rating Scale (PD-CRS)

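### Section 12.2 lists no blinded 5mg pack after week 26, so a participant properly on 5mg at Visit 4 is left with 10mg or stopping study drug

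*Protocol*

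**What the plan says.** Protocol section 12.2 sets a 5mg start and a 10mg target from week 8. It deals with intolerance in two places.

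- **Narrative.** "Any participant reporting significant side effects on 10mg donepezil hydrochloride/day may have their dose decreased back to 5mg/day", and this is "for a further two week period prior to attempting to re-escalate to 10mg/day". No week range is attached, and nothing is said about a failed re-escalation.
- **Dispensing table, weeks 1-26.** Five bottles of 5mg capsules, usable for either dose at the treating team's direction. The increase is conditional on tolerating 5mg, and "If between week 9 and week 26 patient does not tolerate increased dose, it can be reduced back to 5mg".
- **Dispensing table, weeks 26-52, 52-78 and 78-104.** Each row reads "2 bottles (10mg od", with no alternative.

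The same section says of the products: "Active and placebo study medication will be provided either as 5mg or 10mg capsules". It also says that patients "shall return all trial supplies in their original packaging (even if empty) to the Pharmacist every 26 weeks".

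Section 15.1 agrees that escalation is conditional. At the week 8 call (Visit 3) the dose goes up "If there are no adverse events that are deemed by the study team to be dose-limiting". Visit 4, at week 26, includes the item "Review any adverse events" and also dispenses the next pack. Section 17.2 lets the investigator take a participant off study drug for adverse events, while efforts continue to collect follow-up data.

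**The concern.** The plan accepts that some participants will be on 5mg, either because they never went up or because they came back down. It supplies them until week 26, and then the listed supply ends. A site following the table at Visit 4 has a 10mg pack for a person for whom 10mg has been judged unsuitable. Leftover 5mg capsules cannot bridge the gap, because they are returned at that visit.

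Two things are at stake. One is participant welfare: renewed exposure to a dose already found hard to tolerate. The other is adherence: a participant who could have stayed on blinded 5mg may stop instead. Sections 16.1 and 16.2 already anticipate that about half will discontinue medication, and section 17.2 asks that unnecessary withdrawals be avoided. Dose-related intolerance would plausibly be commoner on active drug, though the protocol gives no figure for it. Sites may also improvise in different ways.

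**Working it through.** **1. Do the later packs hold 10mg capsules?** The protocol does not say so outright, and it matters: a pack of 5mg capsules taken two at a time would allow a step-down. The bottle counts help.

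- Weeks 1-26, full titration with 5mg capsules: 8 × 7 × 1 + 18 × 7 × 2 = 56 + 252 = 308 capsules. Over 5 bottles, 308 / 5 = 61.6 per bottle.
- A later 26-week pack with 10mg capsules: 26 × 7 = 182 capsules. Over 2 bottles, 91 per bottle.
- The same pack with 5mg capsules: 2 × 182 = 364 capsules. Over 2 bottles, 182 per bottle.

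The drop from five bottles to two fits a change to 10mg capsules, as does the once-daily 10mg label beside a first row that names 5mg bottles. This is an inference, but a strong one.

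**2. Who is left without a listed pack?** Take the two readings of the step-down rule in turn.

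| Situation | Step-down confined to weeks 9-26 | Step-down open at any week |
|---|---|---|
| Intolerant before week 26 | 5mg available in the first pack | 5mg available in the first pack |
| Still on 5mg at Visit 4 | No 5mg pack listed | No 5mg pack listed |
| First intolerant of 10mg after week 26 | Step-down not offered; 10mg or stop | Step-down offered; no 5mg pack listed |

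The second row does not depend on the reading. The third is a supply gap only on the open reading.

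**3. How long is the later period?** 104 − 26 = 78 weeks, and 78 / 104 = 75%. This is calendar time with only 10mg listed, not a share of participants.

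**4. Does it touch the sample size?** The plan's figures reproduce. With 200 per arm, two-sided 5%, a DRS difference of 4.4 with SD 13.5 (effect size 0.326) gives 90.3% power. An NPI-10 difference of 3.9 with SD 12.0 (0.325) gives 90.1%. Recruitment is 400 / (1 − 0.20) = 500. No input concerns dose or packs, so nothing here changes.

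**5. How much 5mg supply would the remedy use?** At one capsule a day, a participant on 5mg from week 26 to week 104 uses at most 78 × 7 = 546 capsules. The number of such participants is not given. As an assumption for planning only:

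- 5% of 500 = 25 people, at most 25 × 546 = 13,650 capsules
- 10% = 50 people, at most 27,300
- 20% = 100 people, at most 54,600

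**The case against.** The strongest reply is that the step-down sentence sits in a paragraph about titration and should be read with the table's week 9-26 line. On that reading the first pack fully supplies the rule. Before week 26 there is also no missing rule: the first row lets the team hold or return a participant to 5mg, which covers a failed re-escalation and someone who never tolerated 10mg. Both points stand. They reduce the certain part of the concern to the hand-over at Visit 4, but they do not remove it.

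A second reply is that fixed 10mg maintenance, with stopping and continued follow-up for those who cannot take it, is a coherent policy. It is, but section 12.2 does not state it. As written, it permits 5mg up to the day the 10mg pack is dispensed and does not say that permission then ends.

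A third is that the table may be only a default and that study procedures not shown could cover exceptional resupply. That is possible. Section 12.2 does, however, require prescribing according to the protocol, and the protocol lists no such pack.

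A reader might also infer that the dose is doubled automatically at week 26. The documents do not support that: adverse events are reviewed at Visit 4 and a study clinician prescribes.

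**Conclusion.** The point holds in a limited form. On any reading, a participant properly on 5mg at Visit 4 has no listed blinded 5mg pack. If the narrative step-down extends beyond week 26, neither does one who first needs it later. The listed choices are then 10mg or stopping study drug under section 17.2, with follow-up continuing. This rests on the later packs holding 10mg capsules, which the labels and bottle counts support.

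Two stronger readings should be resisted. One is that the step-down rule is undeliverable for 75% of the treatment period. That requires the narrative to be unlimited in time, which the week 9-26 line leaves open. The other is that the gap biases a primary outcome or costs power. The number affected is not stated, no arm difference is shown, and the sample size does not depend on it. The effect is on safety, adherence and consistency between sites, and it is worth correcting.

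**What to change.** In section 12.2, change the rows for weeks 26-52, 52-78 and 78-104 to 10mg once daily, or 5mg once daily if 10mg is not tolerated. Add one sentence: if re-escalation after two weeks fails, or 10mg was never tolerated, the participant continues on blinded 5mg. This extends the plan's own step-down policy and uses 5mg active and placebo capsules that already exist.

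Supply should be a central blinded resupply linked to the participant's kit number. Section 13 ties one kit number to each participant's blinded allocation, so spare packs held at site by arm would strain that system and could threaten the blind.

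The cost is a protocol amendment, extra labelled 5mg packs and a small change to the kit allocation system. Visits, data collection, sample size and analysis stay as they are. If the sponsor does intend 10mg or stopping from week 26, the protocol should say so and confine the narrative step-down to weeks 9-26.
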